5.2 Exclusion Criteria

Subjects with any of the following will be excluded from the study:

1. If female, active pregnancy or breast-feeding or plans to become pregnant during study participation.
2. Subject report of having any medical disease or condition that, in the opinion of the site principal investigator or appropriate sub-investigator, is a contraindication to study participation. This includes any *acute or chronic*

medical disease or condition, defined as persisting 3 months (defined as 90 days) or longer, that would place the subject at an unacceptable risk of injury, render the subject unable to meet the requirements of the protocol, or may interfere with the evaluation of responses or the subject's successful completion of this study.

3. Subject report of taking anticoagulants, or long-term (greater than 14 days) systemic steroids or other immunosuppressive medications
4. Subject report of known allergy to lidocaine.
5. Subject report of known hypersensitivity or allergy to eggs, egg or chicken protein, report of allergy to components of the study vaccine or other components of the study vaccine
6. Subject report of known latex allergy
7. Subject report of a history of severe reactions following previous immunization with licensed or unlicensed influenza virus vaccines
8. Subject report of a history of Guillain-Barre syndrome
9. Subjects who believe they cannot tolerate the bone marrow aspirations without sedation.
10. Subjects with an active infection or that have an acute illness within 72 hours prior to study vaccination. Subject having had an acute illness which is nearly resolved with only minor residual symptoms remaining is allowable if, in the opinion of the site principal investigator or appropriate sub-investigator, the residual symptoms will not interfere with the ability to assess safety parameters as required by the protocol.
11. Subjects who are participating in another clinical trial involving the use of investigational agents or vaccines.

5.3 Handling of Withdrawals

Subjects are free to withdraw from the study at any time. Subjects are provided a revocation form at enrollment with withdrawal procedure clearly explained.

Subjects who do not meet inclusion and exclusion criteria at the second or third bone marrow aspirate visit will not have the aspiration performed and will be withdrawn from the study. Any unresolved adverse events will be followed per Section 9, Assessment of Safety.

Subjects may be taken off study without their consent if the study doctor determines that it is in the subject's best interest not to continue to participate in the study. In addition, the study doctor may remove a subject from study participation if the subject is unable to complete the required study procedures, or if the study is stopped by the institution, the sponsor, or the Food and Drug Administration (FDA) or other health authorities. If the subject is removed from the study, the Principal Investigator or designee will contact the participant to discuss the study stopping procedures.

Participants who withdraw, or are withdrawn or terminated from the study, or are lost to follow-up after study enrollment visit will not be replaced. Participants who consented to the study but did not receive the influenza vaccine will be replaced. These subjects will be considered as screen failures.

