3.2 Outcome Measures

3.2.1 Primary Outcome

Primary Objective Measures: To investigate the longevity of humoral immunity to influenza virus in humans by:

- Determination of the number of influenza-specific antibody secreting cells (ASC) present in the bone marrow prior to vaccination and at 28 days and one year post vaccination.
- Determination of the number of influenza-specific antibody secreting cells (ASC) present in the blood 7 days post-vaccination.
- Determination of the number of influenza-specific memory B cells present in the blood prior to vaccination and at 14 days, 28 days, 90 days, and 365 days post-vaccination.
- Determination of the percentage of subjects achieving seroconversion to each of the three strains contained in the trivalent vaccine. Seroconversion is defined as having a pre-vaccination hemagglutination inhibition (HAI) titer $<1:40$ against a particular strain and a day 28 post-vaccination titer $\geq 1:40$ against the same strain.
- Determination of the percentage of seroconverting subjects who maintain an HAI titer $\geq 1:40$ approximately 365 days after the study vaccination.

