5.1 Inclusion Criteria

For inclusion into the study, a subject must satisfy all of the following criteria:

1. Male or non-pregnant female subjects between 18 and 49 years of age (inclusive)
2. Subjects capable of providing written informed consent prior to initiation of any study procedures.
3. Subjects able to understand and comply with planned study procedures and be available for all study visits.
4. Safety labs
 - a. WBC, within reference range of lower limit of normal of 4,000/uL, and upper limit of normal of 10,000/uL.
 - b. Hemoglobin, within reference range of lower limit of normal of 11.4 gm/dL and upper limit of normal of 16.1 gm/dL.
 - c. Hematocrit, within reference range of lower limit of normal of 33.3% and an upper limit of normal of 46.5%.
 - d. Platelet Count within reference range of lower limit of normal of 150,000/uL and upper limit of normal of 400,000/uL.
 - e. PT/INR, PT below or equal to the upper limit of normal of 13.1 seconds; INR within normal reference range of less than 1.5 (normal range for non-anti-coagulated patients).
 - f. Creatinine within reference range of lower limit of normal of 0.4 mg/dL and upper limit of normal of 1.2 mg/dL.

- g. Potassium), within reference range of lower limit of normal of 3.6 mM and upper limit of normal of 5.1 mM.
5. Heart rate ≥ 55 to ≤ 100 per minute
6. Systolic blood pressure ≥ 90 to ≤ 150 mm Hg
7. Diastolic blood pressure < 90 mm Hg
8. Oral temperature $< 100^{\circ}\text{F}$
9. Respirations even, unlabored, and $> 10/\text{minute}$ to $< 20/\text{minute}$.
10. Female subjects of child bearing potential must have a negative urine pregnancy test at the screening visit, enrollment visit and prior to subsequent bone marrow aspirate procedures. Female subjects of childbearing potential must agree to practice abstinence, use a barrier method of birth control, or use an FDA approved form of birth control
11. Subjects who have not received seasonal flu vaccine for the current year (September – June)

Subjects that have participated in a previous year may be screened for re-enrollment in subsequent second and third year. Subjects that are re-enrolling will be re-consented, re-screened, and given a new identifier. Re-enrolling subjects will be counted towards the enrollment totals for each year. Subjects who report having already received the flu vaccine for the current flu season will be restricted from further study participation.

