- **Day 28 post vaccination study visit (+/- 2 days):** Subjects will have clinical safety labs drawn including a platelet count and hemoglobin and hematocrit (4ml of blood) Females of childbearing potential will have a urine pregnancy test performed, and the test result must be negative for the subject to continue with study participation. The results of the blood tests must be assessed by the study physician as within a healthy range for continued study participation using the most current normal lab ranges, and evaluated for clinical significance of lab values that fall outside of normal range. Subjects will have 64 ml of blood drawn for antibody testing. Vital signs including oral temperature, blood pressure, pulse rate and respiratory rate will be obtained. A health assessment will be performed including an inquiry about any illness or health change since the last study visit. Concomitant medications will be reviewed and updated. An assessment will be made for any adverse events or serious adverse events. Participants will receive a physical exam by a licensed to make medical diagnoses and listed on the Investigator of Record Form as the site principal investigator or sub-investigator. The Adverse Event Report Form will be updated if indicated. Study eligibility criteria will be reviewed by the study nurse and physician and confirmed that the subject meets all inclusion and none of the exclusion eligibility criteria prior to the bone marrow aspirate procedure. [name] as site principal investigator or the sub-investigator will explain the bone marrow aspirate procedure, and the informed consent document for the procedure will be signed by the subject in the presence of [name]. The bone marrow aspirate procedure and aspirate volume will be the same as the same as at study enrollment.
 - Due to the COVID-19 pandemic, all non-essential research was halted in mid-March 2020.
 - One participant had their Day 28 visit halted.
 - We are requesting that the Day 28 window be extended by a maximum of up to 180 days, to allow completion of the follow-up visit for the impacted participant.
 - The participant will be contacted by phone or via encrypted email message to arrange scheduling of subsequent visits.
 - To assist with assessing symptoms, the COVID-19 Screening Questionnaire/Script will be reviewed with participants prior to bringing the participant in for follow-up visits.

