- **Day 365 visit (+/- 3 months):** Subjects will have clinical safety labs drawn including a platelet count and hemoglobin and hematocrit (4ml of blood). Females of childbearing potential will have a urine pregnancy test performed, and the test result must be negative for the subject to continue with study participation. The results of the blood tests must be assessed by the study physician to be within a healthy range for continued study participation using the most current normal lab ranges, and evaluated for clinical significance of lab values that fall outside of normal range. Subjects will have 64 ml of blood drawn for antibody testing. Vital signs including oral temperature, blood pressure, pulse rate, and respiratory rate will be obtained. A health assessment will be performed including an inquiry about any illness or health change since the last study visit. Concomitant medications will be reviewed and updated. An assessment will be made for any adverse events or serious adverse events. Participants will receive a physical exam by a licensed to make medical diagnoses and listed on the Investigator of Record Form as the site principal investigator or sub-investigator. The Adverse Event Report Form will be updated if indicated. Study eligibility criteria will be reviewed by the study nurse and physician and confirmed that the subject meets all inclusion and none of the exclusion eligibility

criteria prior to the bone marrow aspirate procedure. [name] will explain the bone marrow aspirate procedure, and the informed consent document for the procedure will be signed by the subject in the presence of [name]. The bone marrow aspirate procedure and aspirate volume will be the same as the as at study enrollment and at visit day 28.

- It is not anticipated that any of the Day 365 visits will be impacted.

The day 365 post vaccination visit will be the final study visit unless the subject decides to re-enroll in the study. Provided eligibility criteria are met, subjects may re-enroll in the study for a total study participation of up to three years per subject. The day 365 visit may also be the day 0 visit for a subject who is re-enrolling into the study, provided that re-screening of the subject occurs and the subject meets study eligibility criteria for continued study participation. These subjects will receive a new study identifier and a separate research record will be maintained by study staff.

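### Failing the eligibility re-check on a repeat aspirate day means withdrawal from the whole study, so a Day 28 failure discards Day 90 and Day 365 blood outcomes that need no aspirate

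*Combined protocol and SAP*

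**What the plan says.** - **Re-check.** For both the Day 28 and the Day 365 visit, Section 7.3 has the nurse and physician review eligibility, with it "confirmed that the subject meets all inclusion and none of the exclusion eligibility criteria prior to the bone marrow aspirate procedure". No criterion is exempted.
- **Consequence.** Under Section 5.3, a subject who fails at the second or third aspirate visit "will not have the aspiration performed and will be withdrawn from the study". Anyone withdrawn after the enrollment visit is not replaced, and Section 7.4 gives no visit after early termination.
- **Criterion 11.** Section 5.1 admits "Subjects who have not received seasonal flu vaccine for the current year", and its paragraph on re-enrollment adds: "Subjects who report having already received the flu vaccine for the current flu season will be restricted from further study participation". Sections 7.2 and 8.1 give the seasonal vaccine on Day 0.
- **Criterion 1.** Section 5.1 limits age to 18–49.
- **Blood outcomes.** The primary outcomes in Section 3.2.1 include memory B cells in blood at Days 90 and 365, and "Determination of the percentage of seroconverting subjects who maintain an HAI titer" of at least 1:40 at about one year.

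**The concern.** Eligibility on an aspirate day is a question about whether the marrow procedure should go ahead. The protocol attaches to it a consequence for the whole study. A subject who fails on Day 28 because of a temperature, pulse or hemoglobin value loses the aspirate, the Day 90 and Day 365 blood, and the chance of a Day 365 marrow sample.

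The study is about longevity, so its late time points matter most, and Section 11 does not say how outcomes missing through this rule are handled. A return visit after a transient condition is offered at screening (Section 7.1) but is not mentioned for Day 28 or Day 365.

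The rule also cannot be applied as worded, because some of the criteria it re-applies make sense only at entry. Staff are left to decide for themselves which ones count.

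**Working it through.** **1. The plan's own figure.** Section 11.2 needs 25 cross-reactive clonotypes and expects one in about 50% of donors: 25 / 0.50 = 50 donors. With 10% dropout, 50 / 0.90 = 55.6, and 55 × 0.90 = 49.5. The planned 55 therefore reproduces to within one donor. The exact slack is 5 of 55, or 9.1%. This allowance concerns donors whose clones are followed in marrow from one month to one year.

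**2. The sections side by side.**
- *Criterion 11 against Day 0 vaccination.* Section 5.3 counts people who consent but are not vaccinated as screen failures, so everyone who reaches Day 28 has had this season's vaccine. Essentially all of them fail criterion 11. The September–June limit leaves it unclear for July and August. At Day 365 the study dose usually belongs to the previous season.
- *Criterion 1 against a one-year follow-up.* If ages are uniform over the 32 years 18–49 (assumption), 1/32 = 3.1% turn 50 within a year, and 55 / 32 = 1.7 subjects. About 1.7 × 28/365 = 0.13 of these would do so by Day 28, so nearly all would arise at Day 365.
- *Laboratory values.* Section 5.1 sets fixed ranges. Section 7.3 lets the physician judge the clinical significance of values outside the normal range. Sections 7.3 and 8.2 repeat only platelets, hemoglobin and hematocrit, so WBC, PT/INR, creatinine and potassium cannot be confirmed.
- *Vital signs.* Section 5.1 requires respirations above 10 per minute, while Section 8.1 allows 10. Section 5.1 has a diastolic limit and Section 8.1 lists none.

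**3. What each failure costs.**

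| Failure at | Lost under the rule |
|---|---|
| Day 28 | Day 28 marrow, Day 90 blood, Day 365 blood, Day 365 marrow |
| Day 365 | Day 365 marrow and, at most, that day's blood |

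Whether the failing visit's own research blood is kept depends on the order of procedures, which the protocol does not fix. Day 365 is the last visit of a participation year, so no later blood remains to be lost.

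**4. Subjects losing later blood.** Let f be the share failing a same-day criterion at Day 28. The documents give no value for f, so these are assumptions. Expected number = 55 × f:
- f = 2%: 1.1
- f = 5%: 2.75
- f = 10%: 5.5

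**5. Marrow pairs, for comparison.** If the same share fails at each of the two repeat aspirate visits, complete pairs = 55 × (1 − f)²:
- f = 2%: 52.8
- f = 5%: 49.6
- f = 10%: 44.6

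Pairs fall below 50 once f exceeds 1 − √(50/55) = 4.7%, before any other dropout. A missed aspirate breaks the pair whether or not the subject stays in blood follow-up.

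**The case against.** **A reader might infer that every participant is lost at Day 28.** The wording allows it, but the rest of the protocol does not. It schedules Day 28, 90 and 365 visits for vaccinated subjects, and Section 7.3 reports three participants whose Day 90 visit was halted by the pandemic. Those three had not been withdrawn at Day 28. The contradiction is real, but it is not applied literally.

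**A reader might infer that any failure loses all later blood, or that the rule overruns the 10% dropout allowance.** The first holds only for Day 28. The second depends on a failure rate that the documents do not give: at 2% per visit the loss is 1 − 0.98² = 4%, well inside the allowance. The allowance also concerns marrow pairs, which continued blood follow-up does not restore.

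**A reader might call the loss informative missingness.** It is plausible. By Day 28 the study has taken 10 + 3 × 64 + 30 = 232 ml of blood and marrow, Section 2.3.1 names anemia as a risk, and hemoglobin is re-measured. But the documents show no link between failing a same-day criterion and antibody longevity, so this remains a possibility.

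**There is some flexibility.** Physician judgement on laboratory values may prevent some failures. A re-check within the visit window (±2 days at Day 28, ±3 months at Day 365) is neither offered nor forbidden. The pandemic text in Section 7.2 lets a participant decline a particular procedure. These points may lower the failure rate, but they do not change what follows once a subject is judged to have failed.

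**Conclusion.** The point stands in two parts. First, Sections 5.1, 5.3 and 7.3 contradict the design through criteria 1 and 11, and the aspirate-day laboratory and vital-sign requirements do not agree across Sections 5.1, 7.3 and 8.1. This is a drafting fault that needs reconciling, not a forecast of 100% loss.

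Second, the withdrawal rule discards Day 90 and Day 365 blood after a Day 28 failure, although primary outcomes depend on that blood and need no aspirate. At assumed failure rates of 2%, 5% or 10%, about 1, 3 or 5–6 of 55 enrollments are affected. The direction of the loss follows from the text; its size rests entirely on the assumed rate. A Day 365 failure puts only that day's samples at risk.

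**What to change.** - **Entry-only criteria.** In Sections 5.3 and 7.3, mark criteria 1 and 11 as entry-only for the repeat-aspirate check within a participation year. They still apply at re-enrollment.
- **Aspirate-day criteria.** Reconcile Sections 5.1, 5.3, 7.3 and 8.1 on which safety criteria and laboratory values govern an aspirate day. The sponsor's medical team decides which.
- **Missed aspirate versus withdrawal.** Record an aspirate not done separately from withdrawal from the study, so that a subject who misses one can, with consent and physician agreement, stay in the blood follow-up already scheduled. The pregnancy rule in Section 9.3.3 and other safety withdrawals stay unchanged.
- **Analysis.** Use all available blood data: the mixed model already planned in Section 11 for continuous outcomes and, for the binary HAI maintenance outcome, the number missing reported beside the percentage.

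This keeps blood data and, after a Day 28 miss, the chance of a Day 365 marrow sample. It does not restore missed Day 28/Day 365 marrow pairs, so it does not protect the Section 11.2 clone count.

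The cost is a protocol amendment with IRB approval (Section 14.2); the blood draws are already scheduled. Because enrollment ended on March 31, 2020, the change reaches only the remaining visits and the reporting and analysis of earlier withdrawals.

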5.4 Termination of Study

The sponsor reserves the right to terminate the study at any time for clinical or administrative reasons. Reasons for termination include, but are not limited to, study closure due to internal safety monitoring review and recommendation, or at the discretion of DMID.

6 STUDY INTERVENTION PRODUCT

6.1 Study Product Description

Each flu season, the vaccine used in this study will be a licensed seasonal inactivated influenza vaccine for intramuscular injection that is approved by the FDA. The vaccine product used will depend upon supply stocked by the Emory University Hospital Investigational Drug Services (IDS).

6.1.1 Acquisition

The licensed vaccine will be provided by the Emory University Hospital Investigational Drug Pharmacy.

6.1.2 Formulation, Packaging, and Labeling

These vaccines are typically provided in pre-filled syringes (clear syringe plunger rod), 0.5 ml. If pre-filled syringes are not available from the manufacturer, the study product will be provided in a latex free single-dose vial, one vial per carton, 1 vial containing 0.5 ml dose.

The vaccine used in this study is the licensed seasonal inactivated influenza vaccine and will be supplied by Emory University Hospital Investigational Drug Services (IDS) in a pre-filled syringe or single-dose vial placed in a clear plastic bag labeled with the DMID protocol number, subject name, study ID, and dosing instructions per the prescription signed by the investigator's designee.

6.1.3 Product Storage and Stability

Per the package insert from the manufacturer, the seasonal inactivated influenza vaccine will be stored at 2-8 degrees C (35.6-46.4 degrees F). Vaccine will be stored at the Emory University Hospital Investigational Drug Services in a study specific designated location, within a temperature-controlled refrigerator. The temperature of the storage unit will be 24-hour, continuously recorded and monitored.

6.2 Dosage, Preparation and Administration of Study Intervention Product

A vaccine dose of 0.5 mL will be administered by the clinical research nurse intramuscularly (IM) in the subject's preferred deltoid (upper arm) per the manufacturer's instructions.

6.3 Modification of Study Intervention Product for a Participant

All subjects will receive 0.5 ml of vaccination. No modifications will occur for participants.

6.4 Accountability Procedures for the Study Intervention Product(s)

Emory Investigational Drug Service, as delegated by the study principal investigator, will maintain and monitor the inventory of the influenza vaccine per good clinical practice. Emory Investigational Drug Service will maintain records of study product acquisition, dispensing, storage and destruction.

6.5 Assessment of Participant Compliance with Study Intervention Product

Each participant will be assessed for compliance with the influenza vaccination via his or her receipt of 0.5ml of vaccine without immediate reaction.

6.6 Concomitant Medications/Treatments

Persons taking anticoagulants, long-term aspirin therapy, or long-term (greater than 14 days) systemic steroids will be excluded from study participation. Subjects with chronic medical conditions that require immunosuppressive medications which could alter immune function, or with chronic medical conditions such as diabetes or hypertension, will not be allowed to participate on the study. The medication history will be reviewed and updated at every study visit to ensure that subjects are not taking the medications prohibited for study participation.

Prohibited medications for this study include the following: tacrolimus, cyclosporine, mycophenolate mofetil, azathioprine, infliximab, entercept, oral or intravenous steroids such as methylprednisolone, dexamethasone, prednisone; orencia, methotrexate, rapamycin, heparin, warfarin, low molecular weight heparins such as enoxaparin, and any medication not otherwise listed that, in the opinion of the investigator, meets the criterion as a prohibited medication for this study. The use of topical or inhaled steroids is allowed.

